### *Multiplicity*

N/A

### *Power/Sample Size*

Sample size estimates have been made using BOLD signal changes extracted from regions of interest in the data set shown in Figure 2 and analyzed with fMRIpower (32). Inclusion of 25 participants will provide at least 80% power to detect a between-group difference of 0.48 to 0.72 standard deviation units (analogous to Cohen's d) in the regions of interest. This is sufficient power to resolve significant effects of disease (chronic cough) on ATP and capsaicin evoked brain activations in brainstem nuclei (as shown in Figure 2, data collected from n=24 with one additional participant excluded because of excessive head movement during scanning). Males and females will be included in the study.

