## **Objectives & Hypotheses**

To identify the neural circuits involved in ATP-dependent cough sensitization in humans by determining whether ATP-sensitive pathways in the brainstem and brain are altered in patients with chronic cough.

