### **Study Design**

The study will involve 25 participants with cough hypersensitivity and 25 age and sex matched healthy controls. All participants will provide written informed consent to participate in the study, which will be approved by the Melbourne Health Human Research Ethics Committee (Australia). Before inclusion, all participants undergo screening interviews to ascertain their eligibility for the study. All participants will be non-smokers with no history of neurological disease or any recent history (over 8 weeks) of acute respiratory infections. Cough hypersensitive participants will be recruited from respiratory specialist clinics and included if they have experienced chronic cough (coughing for over 8 weeks) and are considered idiopathic/ refractory coughers (to avoid the confounds of heterogeneity of precipitating diseases). Healthy control participants will have no history of chronic respiratory disease and will be individually age and sex matched to each cough hypersensitive participant.

Participants will attend two experimental sessions. The first is used to ascertain their individual sensitivities and tolerances to inhaled challenges with capsaicin and ATP

(psychophysical testing session) and the second to determine their brain responses to challenge stimuli (brain imaging session). This is not an interventional study but rather a comparison between responses in healthy control participants versus patients with chronic cough syndrome.

All participants will first undergo a psychophysical testing session where their level of sensitivity to capsaicin and ATP is measured using a method of limits approach. The following measures of sensitivity are determined: stimulus dose evoking 2 coughs (C2), the stimulus dose required for the initial detection of an urge to cough (Cu) and the maximal suppressive stimulus dose where a participant can resist coughing (Smax). Patients will provide subjective measures of their urge-to-cough using an eleven point numerical rating scale (0, no urge-to-cough; 10, maximum urge-to-cough) evoked by single breath challenges with tussive stimuli. The capsaicin and ATP solutions are nebulized to participants via a

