### *Statistical Methods*

Statistical analysis of psychophysical parameters will be performed with SPSS 22.0. Independent t- tests will be used to test the effects of group on C2, Cu and Smax thresholds. A repeated-measures ANOVA is used to test the effects of group, dose and their interaction on urge-to-cough ratings in response to random stimulus challenges. Independent t-tests will be used to assess group effects on capsaicin/ ATP doses and urge-to-cough ratings associated with the fMRI scanning.

fMRI image analysis will be performed with FEAT, version 5.98. Regressors for each dose of capsaicin/ ATP and rating events will be included in a general linear model that also includes motion parameters and confound variables to take account of physiological noise. Contrasts for capsaicin/ ATP doses will be averaged across the three scans for each participant and used in the analysis of group and between-group effects. Group contrasts include high doses for all participants (Like-Behaviour), and activation levels will be tested for correlations with Cu and frequency of coughing during repeated stimulus challenges. Higher level analyses will be carried out for inter-group averaging and between-group comparisons. Z (Gaussianised T/F) statistic images are thresholded to define clusters of contiguous voxels activated at a significance level of  $Z > 2.3$ . To correct for multiple comparisons, a corrected cluster probability threshold (based on Gaussian Random Field Theory of  $p < 0.05$ ) is applied. Between-group contrasts are made using two different comparisons: i) during the inhalation of Smax for all individuals in both groups (matched urge-to-cough sensation). Activation levels associated with Smax doses are tested for relationships with the Cu threshold and the frequency of coughing during the psychophysical sessions.

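### The stated 80% power for a between-group difference of 0.48 SD is not reproduced with 25 per group: at an assumed 5% level it is 38% (two-sided) or 51% (one-sided)

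*Combined protocol and SAP*

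**What the plan says.** The Power/Sample Size section rests the sample size on one statement: "Inclusion of 25 participants will provide at least 80% power to detect a between-group difference of 0.48 to 0.72 standard deviation units". It likens this unit to Cohen's d and says the estimates come from fMRIpower, applied to region-of-interest BOLD changes in the pilot data (n=24 analysed). It concludes: "This is sufficient power to resolve significant effects of disease (chronic cough) on ATP and capsaicin evoked brain activations in brainstem nuclei". It states no alpha, sidedness or test, and does not say whether 25 is per group.

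Study Design settles the group size: "The study will involve 25 participants with cough hypersensitivity and 25 age and sex matched healthy controls". It adds that controls are "individually age and sex matched to each cough hypersensitive participant".

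Statistical Methods describes the imaging comparison only in general terms: "Higher level analyses will be carried out for inter-group averaging and between-group comparisons". The threshold is Z > 2.3 with cluster correction at p < 0.05, and nothing ties it to the power figure. For the other two-group comparisons the section names unpaired tests, for example: "Independent t-tests will be used to assess group effects on capsaicin/ ATP doses and urge-to-cough ratings associated with the fMRI scanning".

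**The concern.** A difference of about half a standard deviation is small for two groups of 25, so 80% power at 0.48 SD looks too high. The range is also odd in itself. With one sample size, one alpha and one test, Cohen's d has a single value at which power is 80%. A range implies that the scale, the test or the alpha varied between regions, or that the unit is not Cohen's d. The text does not explain which.

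This is the only justification of the sample size. If the label is right, a true difference of 0.48 SD in one region would be missed 62% of the time two-sided (100 − 38) or 49% one-sided (100 − 51), against the 20% or less that the plan promises. If the label is wrong, the plan gives no power for its main comparison. In both cases a reader who trusts the statement could take a null group result as evidence that ATP pathways are unaltered, which is the study's central question.

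**Working it through.** **Inputs from the plan.** 25 per group (Study Design); differences of 0.48 and 0.72 SD and power of at least 80% (Power/Sample Size).

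**Assumptions, because the plan is silent.** A 5% level, one region, no correction over regions or voxels, and an unpaired t-test. Two-sided and one-sided results are both shown.

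**Step 1: the plan's figure as labelled.** For n per group the noncentrality is d × √(n/2), with 2n − 2 degrees of freedom.

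- At 0.48 SD: 0.48 × √12.5 = 1.697
- At 0.72 SD: 0.72 × √12.5 = 2.546
- Critical t on 48 df: 2.011 two-sided, 1.677 one-sided

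| Quantity | Two-sided 5% | One-sided 5% |
|---|---|---|
| Power at 0.48 SD | 38.3% | 51.1% |
| Power at 0.72 SD | 70.3% | 80.6% |
| Difference with 80% power | 0.81 SD | 0.71 SD |
| n per group for 80% at 0.48 SD | 70 | 55 |

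A normal approximation at 0.48 SD agrees: Φ(1.697 − 1.960) = 39.6% two-sided and Φ(1.697 − 1.645) = 52.1% one-sided. With 25 per group, 80% power at 0.48 SD would need a one-sided alpha of about 0.20.

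**Step 2: a paired analysis.** With within-pair correlation r, the effect on the scale of the pair differences is d / √(2(1 − r)). A one-sample t-test on 25 pairs reaches 80% power at 0.584 two-sided or 0.512 one-sided. Solving, r = 1 − d² / (2 × threshold²):

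- 0.48 SD, two-sided: 1 − 0.2304 / (2 × 0.3411) = 0.66
- 0.48 SD, one-sided: 1 − 0.2304 / (2 × 0.2621) = 0.56
- 0.72 SD, two-sided: 1 − 0.5184 / (2 × 0.3411) = 0.24
- 0.72 SD, one-sided: 1 − 0.5184 / (2 × 0.2621) = 0.01

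The plan gives no within-pair correlation and describes no paired BOLD model.

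**Step 3: other readings of the 25, at 0.48 SD and 5%.**

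| Reading | Two-sided | One-sided |
|---|---|---|
| 25 in total (normal approximation) | 22% | 33% |
| 50 per group | 66% | 77% |
| One-sample, n = 25 | 63% | 75% |

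None reaches 80%. The readings that do, such as a one-sample n of 50, or 50 per group at one-sided 10%, do not match the comparison named in the plan.

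**Step 4: relation to the planned image analysis.** As an illustration only, one can set a one-sided alpha equal to the tail beyond Z = 2.3 (0.0107). An unpaired test then has 26% power at 0.48 SD and 57% at 0.72 SD, with 80% at 0.91 SD. Cluster inference is not equivalent to this test, so none of these figures is the power of the cluster-corrected analysis.

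**The case against.** The strongest objection concerns direction. The Clinical hypothesis section expects ATP to enhance activation, the Preliminary Data section expects upregulation in patients, and Z > 2.3 is an upper-tail threshold. A one-sided calculation is therefore plausible, and on it 0.72 SD gives 80.6%, almost exactly the stated upper end. That part stands: on this reading only the lower end fails. But the plan states no one-sided test, its objective is non-directional ("determining whether ATP-sensitive pathways in the brainstem and brain are altered in patients with chronic cough"), and one-sided power at 0.48 SD is still only 51%.

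A second objection is that the fMRIpower settings are not given and the unit is only likened to Cohen's d, so the range may be correct on some other scale. This also stands as a possibility. It means that 38% cannot be called the study's power; it is the power of the comparison as labelled, under the assumptions listed. It does not rescue the sentence, because the between-group label would then be wrong.

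Third, individual matching could support a paired analysis. The required correlation of 0.56 to 0.66 in BOLD response is neither stated nor supported in the plan.

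Finally, nothing in the plan says that a null result will be read as no difference. That consequence is a risk of misreading, not something the authors propose.

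**Conclusion.** The concern holds. As labelled, 25 per group does not give 80% power at 0.48 SD: power is 38% two-sided or 51% one-sided, and 80% is reached at 0.81 or 0.71 SD. At 0.72 SD the claim is reproduced one-sided (81%) but not two-sided (70%). These figures assume an unpaired test in one region at an uncorrected 5% level. Pairing would change them only with a within-pair correlation that the plan does not give.

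Confidence is high that the statement is not reproducible as labelled. Whether the number or the label is at fault cannot be settled from the documents. The point should be fixed; it does not call for a change of design.

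**What to change.** In Power/Sample Size, state alpha, sidedness, n per group, paired or unpaired test, effect scale and the fMRIpower inputs. Then take whichever branch applies.

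1. **If a between-group Cohen's d is meant**, restate the claim along these lines: with 25 per group, for an unpaired comparison in a single prespecified region at two-sided 5% without correction for multiple regions, 80% power is reached at 0.81 SD; power is 38% at 0.48 SD and 70% at 0.72 SD. If the fMRIpower calculation was in fact one-sided, say so and use 0.71 SD, 51% and 81%. If it assumed pairs, give the within-pair correlation and describe the paired model in Statistical Methods.
2. **If the range is one-sample or on another scale**, relabel it and give the between-group figure separately.

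In both cases, add that these are single-region figures and do not describe the power of the cluster-corrected analysis. Replace the unqualified closing claim of sufficient power, and say that a non-significant group difference will not be read as evidence of no difference.

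Optionally, report region-level group differences with 95% confidence intervals. For an unpaired single-region comparison the half-width is about 2.011 × √(2/25) = 0.57 SD.

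The cost is a text change and a less favourable stated detectable difference. No participants or scans are added. The optional intervals would be a small extra region-level analysis.

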Sensory inputs from the upper and lower airways to the brainstem are relayed to higher brain regions where they are integrated in subcortical nuclei and then mapped to the cingulate, insula, orbito-frontal and somatosensory cortices in the cerebrum (9). Studies using fMRI of the human brain during challenges with inhaled airway irritants have shown these areas to be important for the different sensory and motor responses that accompany coughing. Importantly, these central neural pathways function differently in chronic cough patients (10). Thus, responses to sensory inputs are exaggerated while those needed to suppress (control) coughing are depressed. This exciting discovery has shed an entirely new perspective on problematic cough, suggesting that pulmonary conditions that lead to coughing may do so by changing the way in which the central nervous system responds to sensory inputs. The striking parallels regarding peripheral and central sensitization which link cough and pain syndromes have prompted recent collective effort to more completely understand the processes leading to these neural dysfunction (11).

Despite this important understanding of the process of CHS, the most important unmet need relates to the lack of effective antitussives. Clinically, amitriptyline and gabapentin are used as cough suppressants with central effects potentially on CHS pathways that remains to be determined, but their effect is not uniform in all patients with chronic cough (12). However, more recently, a blocker of the ATP receptor, P2X3, Gefapixant (600 mg twice a day for 14 days), has been shown to be extremely effective in suppressing the chronic cough of patients with an idiopathic cough, with a reduction in cough frequency by 75% when compared to placebo with daytime cough frequency reduced from a mean 37 coughs per hour to 11 coughs per hour (13). These results were confirmed in another randomized, double-blind, placebo-controlled, Phase 2b crossover study using lower doses of Gefapixant (50 mg, 100 mg, 150 mg and 200 mg twice daily for four days) demonstrated significant reduction in cough frequency, including at the lowest dose of 50 mg twice daily (14). However, contrasting with this positive effect of Gefapixant, studies using TRP receptor blockers such as TRPV1 and TRPA1 antagonists have failed to show any efficacy in chronic

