### *Variables/Time Points of Interest*

Two types of data will be collected, (1) Blood Oxygen Level Dependent signal data collected during fMRI scans and used to determine regional brain activity, and (2) psychophysical data during preliminary testing sessions and during fMRI scanning. The latter includes the stimulus dose evoking 2 coughs (C2), the stimulus dose required for the initial detection of an urge to cough (Cu) and the maximal suppressive stimulus dose where a participant can resist coughing (Smax). As part of the clinical work up of the patients we will also collect

subjective patient scores of their cough severity and quality of life, using validated tools (the Leicester Cough Questionnaire (LCQ)) which can be also used to help interpret fMRI data. The primary variable of the study is the stimulus delivered (ATP versus capsaicin) compared between cough patients and healthy controls, assessing the differential outcomes on BOLD signal changes and associated psychometrics.

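### The primary comparison reads as ATP versus capsaicin between groups, but the stated 80% power is for an unnamed between-group contrast and cannot be taken as the power for it.

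*Combined protocol and SAP*

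**What the plan says.** All sections cited are in the combined protocol and SAP.

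- **Study Design:** "The study will involve 25 participants with cough hypersensitivity and 25 age and sex matched healthy controls".
- **Variables/Time Points of Interest:** "The primary variable of the study is the stimulus delivered (ATP versus capsaicin) compared between cough patients and healthy controls". The section adds that differential effects will be examined in the imaging signal and in the psychometric measures. No contrast, brain region or test is named.
- **Power/Sample Size:** "Inclusion of 25 participants will provide at least 80% power to detect a between-group difference of 0.48 to 0.72 standard deviation units" in the regions of interest, followed by "This is sufficient power to resolve significant effects of disease (chronic cough) on ATP and capsaicin evoked brain activations in brainstem nuclei". The estimates come from the Figure 2 data set (n=24). The section gives no alpha, sidedness or within-person correlation, and does not name the contrast.
- **Objectives & Hypotheses:** the aim includes "determining whether ATP-sensitive pathways in the brainstem and brain are altered in patients with chronic cough", which does not in itself require a contrast against capsaicin.
- **Statistical Methods:** the capsaicin and ATP contrasts are "averaged across the three scans for each participant and used in the analysis of group and between-group effects". Between-group comparison is made at each person's Smax. No ATP-minus-capsaicin contrast compared between groups is written down.

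**The concern.** Comparing ATP with capsaicin, and then comparing that difference between patients and controls, is a group-by-stimulus interaction. It differs from a plain group difference in two ways. Any disease effect common to both stimuli cancels. The relevant SD is that of a within-person difference, which depends on how strongly a person's two responses correlate. A power figure for one contrast therefore does not carry over to the other.

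The power statement speaks of disease effects on activations evoked by the two stimuli and does not mention their difference. A reader will probably take the 80% as applying to the primary comparison. Calling a patient-control difference specific to ATP, as opposed to general hypersensitivity, depends on the differential test. In the current text that test is neither written out nor given a power figure.

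**Working it through.** **Inputs.** 25 per group (Study Design). Effects of 0.48 and 0.72 SD and power of at least 80% (Power/Sample Size). Assumed because the documents do not state them: alpha 0.05 for one region, tested both one- and two-sided; rho, the within-person correlation of ATP and capsaicin responses, from 0 to 0.7; k, the capsaicin disease effect as a fraction of the ATP disease effect, at 0, 0.25 and 0.5; equal SD for the two stimuli.

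**Step 1: the plan's own figure.** For a two-sample t-test with n per group, the noncentrality is d × √(n/2) on 2n − 2 degrees of freedom. Here √(25/2) = 3.536 and there are 48 degrees of freedom.

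| d | Noncentrality | Two-sided power | One-sided power |
|---|---|---|---|
| 0.48 | 1.70 | 38% | 51% |
| 0.72 | 2.55 | 70% | 81% |

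The smallest d with 80% power is 0.81 two-sided and 0.71 one-sided. Only the upper end of the printed range reproduces, and only one-sided. Treating the data as 25 one-sample or paired values still gives only 63% (two-sided) or 75% (one-sided) at 0.48.

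**Step 2: the same threshold for the differential contrast.** Let each person's outcome be D = ATP response − capsaicin response. If each response has SD 1, then SD(D) = √(2(1 − rho)). Comparing D between groups is again a two-sample test with 25 per group, so 80% two-sided power needs 0.81 SD of D. In single-stimulus SD units that is 0.809 × √(2(1 − rho)):

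- rho 0: 0.809 × 1.414 = 1.14
- rho 0.5: 0.809 × 1.000 = 0.81
- rho 0.7: 0.809 × 0.775 = 0.63

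**Step 3: differential power relative to a simple effect.** Suppose the simple ATP group effect has exactly 80% power, so d = 0.809. The standardised differential effect is d(1 − k)/√(2(1 − rho)). For example, at k = 0.5 and rho = 0.5 it is 0.809 × 0.5/1 = 0.404, which gives 29%. Two-sided power:

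| k | rho 0 | rho 0.5 | rho 0.7 |
|---|---|---|---|
| 0 | 51% | 80% | 95% |
| 0.25 | 32% | 56% | 77% |
| 0.5 | 17% | 29% | 44% |

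**Step 4: break-even.** The two powers are equal when (1 − k)² = 2(1 − rho), that is, rho = 1 − (1 − k)²/2. This gives rho = 0.50, 0.72 and 0.875 for k = 0, 0.25 and 0.5. Above those values the differential test is the more powerful one.

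**The case against.** The strongest reply is that the plan may not intend an interaction at all. The section on variables names a primary variable, not a test. The objective asks whether ATP-sensitive pathways are altered in patients, and Statistical Methods lists group comparisons without a differential contrast. On that reading the power statement is aimed at the planned comparison. This stands as far as it goes: the primary question is unclear across the four sections. It does not rescue the printed figure, because a simple two-sided group comparison has only 38% to 70% power over that range. Individual matching could bring 0.48 SD up to 80% only with a paired analysis and a within-pair correlation of about 0.66 (0.56 one-sided), and no paired fMRI test is specified.

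Three stronger readings are tempting, and the documents do not support them.

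- *A reader might infer that the 80% is for a group difference within one stimulus.* The power section does not name its contrast, so this is inference.
- *A reader might infer that differential power is necessarily far lower.* It depends on rho and k, which are not given. At k = 0 with rho of 0.5 or more there is no loss, and a negative k would raise power.
- *A reader might expect a large shared effect, since the background says that "responses to sensory inputs are exaggerated while those needed to suppress (control) coughing are depressed".* That describes general sensitisation and does not quantify a shared effect in these brainstem regions. Comparing groups at individually set Smax, intended to equalise the urge to cough, may reduce it. The hypothesis under Preliminary Data, that ATP gains access to jugular pathways in patients, fits a small k.

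Nor does any section say that a null differential result would be reported as adequately powered evidence of no ATP-specific change. That risk is possible, not planned.

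**Conclusion.** The point holds in limited form. The primary comparison reads most naturally as group-by-stimulus, the power statement does not identify its contrast, and the printed 80% therefore cannot be taken as power for the primary comparison. With 25 per group, 80% power requires 0.81 SD (two-sided) or 0.71 SD (one-sided) of whatever contrast is tested. That conclusion assumes a two-sample t-test at 5% in one region and does not depend on rho or k.

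How the differential contrast compares with a simple group effect is undetermined. From a benchmark of 80% for the simple ATP effect, it has 51% to 95% at k = 0 and 17% to 44% at k = 0.5, for rho 0 to 0.7. These are assumed ranges, not estimates for this study.

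**What to change.** 1. Reconcile Objectives & Hypotheses, Variables/Time Points of Interest, Statistical Methods and Power/Sample Size by naming one primary contrast and its region or regions. Choose it on scientific grounds, not by which contrast turns out to have more power.
2. In Power/Sample Size, replace the printed statement with the figure for that contrast: 80% at 0.81 SD, two-sided 5%, 25 per group. State alpha, sidedness and the SD used. Do not retain 0.48 to 0.72 SD as valid for the simple effect.
3. If the differential is primary, write the ATP-minus-capsaicin contrast, compared between groups, into Statistical Methods and report it with a confidence interval. Take rho from the Figure 2 data if the same people received both stimuli, which the text does not state. Preliminary Data describes healthy participants, so those data cannot inform k; show power over an assumed range of k.

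The cost is one recalculation, partly from data already held, and a few sentences in the sections named. The downside is a less favourable stated power. Enrolment does not change.
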